**Sponsor PMS Contact for Reporting of a Serious Adverse Event (SAE)**

GSK Biologicals Central Back-up PMS Contact for Reporting SAEs: refer to protocol [8.4.1](#).

PMS Contact for Reporting SAEs: refer to the local study contact information document.

**CONFIDENTIAL**208710 (EPI-HPV-077 VS KR PMS)  
Protocol Amendment 1 Final**SYNOPSIS**

Detailed Title	A prospective, observational, multi-centre, post-marketing surveillance (PMS) to monitor the safety of GlaxoSmithKline (GSK) Biologicals' human papillomavirus (HPV)-16/18 vaccine, Cervarix when administered to 9-25 years old subjects according to the approved Prescribing Information in Korea
Indication (Amended: 14 May 2018)	Cervarix is a vaccine indicated for active immunisation against HPV infection in males and females 9-25 years old as 3 doses, 0, 1 and 6 months schedule. Children and adolescents 9-14 years old can be vaccinated with 2 doses, 0 and 6-12 months schedule.
Objective	To assess the safety of GSK Biologicals' human papillomavirus (HPV)-16/18 vaccine, Cervarix , in terms of frequency and intensity of AEs and SAEs when administered according to the local Prescribing Information.
Rationale for the PMS	In Korea, GSK Biologicals' human papillomavirus (HPV)-16/18 vaccine, Cervarix was approved in July 2008. As per Ministry of Food and Drug Safety (MFDS) (Korea) requirements, this post-marketing surveillance (PMS) is being conducted to collect safety information on the use of Cervarix , in at least 600 Korean subjects within 30 days after the vaccination when administered according to the approved PI in Korea in a real health care setting over a 4 year period.
PMS design (Amended: 14 May 2018)	
 
• PMS design: A prospective, observational, non-comparative, multi-centre PMS in Korea.
 
• Study population: 9-25 years old males and females.
 
• Vaccination schedule: Three doses of Cervarix will be administered as per the local Prescribing Information in Korea. Subjects aged 9-14 years old can be vaccinated with two dose schedule.
 

The recommended schedule is as follows:

- Vaccination: The 9-25 years old subjects should be administered *Cervarix* with 3 doses (**0.5mL each**), 0, 1, and 6 months schedule. The 9-14 years old subjects can be vaccinated with 2 doses, 0 and **6-12 months** schedule.  
*In the 2-doses schedule, if the second dose is administered before 5 months after the first dose, the third dose vaccination is required. In the 3 doses schedule, if the vaccination schedule requires flexibility, the second dose can be administered*

**CONFIDENTIAL**

208710 (EPI-HPV-077 VS KR PMS)  
Protocol Amendment 1 Final

***between 1 and 2.5 months and the third dose can be administered between 5 and 12 months after the first dose.***

Note: The subject/subject's parent's/ Legally acceptable representative's (LAR) signature in the ICF/IAF signifies enrolment of the subject into the PMS. The ICF/IAF is for the collection and handling of safety information and **not** for the vaccination procedure.

- Safety monitoring:
  - Recording of all AEs during the 30 day period (**Day 1 to Day 30**) using diary cards after each dose of *Cervarix* is administered.
  - Recording of SAEs reported throughout the PMS period up to 30 days (**Day 1 to Day 30**) after the last dose of *Cervarix* is administered during the subject's participation in the PMS.
- Blood Samples: No blood samples will be collected in this PMS.
- Primary completion Date: last visit of Epoch 1  
Refer to GLOSSARY OF TERMS for the definition of PCD.
- End of Study (EoS): Last subject's last visit. (Follow up after the last dose)  
Refer to GLOSSARY OF TERMS for the definition of EoS.
- Duration of the PMS: The intended duration of this study is approximately 4 years.
  - Epoch 001: Prospective data collection starting at vaccination dose 1 and ending at follow up after **last dose**.

The below table presents the study group and the epoch foreseen in the PMS study.

**Synopsis table 1 Study group and epoch foreseen in the study**

Study group	Number of subjects	Age (Min/Max)	Epoch 001
HPV Group	Approx 600	9/25 years	X

- Pregnant subjects: Pregnant subjects who receive *Cervarix* inadvertently or subjects who become pregnant within 30 days after any vaccination dose will be followed up to determine the pregnancy outcome.

**CONFIDENTIAL**

208710 (EPI-HPV-077 VS KR PMS)  
Protocol Amendment 1 Final

Pregnancy outcome including the status of the mother and child will be forwarded to GSK. Generally, follow-up should be no longer than 6 to 8 weeks following the estimated delivery date, if possible.

- Type of PMS: Self-contained.
- Data collection: Standardised hard copy Case Report Form (CRF). SAEs, ADRs and pregnancy information will be collected by using the SAE, ADR and Pregnancy Reporting Form.
- All adverse events reported during the 30-day post-vaccination follow-up period and all SAEs reported up to 30 days (*Day 1 to Day 30*) after the last dose administered during the PMS will be collected as part of safety data in this PMS. These adverse events will be further classified by GSK at the time of statistical analyses as expected/unexpected based on the current Prescribing Information.
- As per the MFDS (Korea) requirements, safety information from a total of at least 600 evaluable subjects is needed for this PMS. Therefore, a total of at least 600 evaluable subjects will be enrolled over a period of 4 consecutive years.
- Occurrence of AEs during the 30-day (*Day 1 to Day 30*) follow-up period after each vaccine dose.
- Occurrence of any SAE reported throughout the PMS period up to 30 days (*Day 1 to Day 30*) after the last dose of *Cervarix* administered during subject's participation in the PMS.

**CONFIDENTIAL**

208710 (EPI-HPV-077 VS KR PMS)

Protocol Amendment 1 Final

**LIST OF APPENDICES**

	PAGE
APPENDIX A AMENDMENTS ADMINISTRATIVE CHANGES TO THE PROTOCOL.....	56

**CONFIDENTIAL**208710 (EPI-HPV-077 VS KR PMS)  
Protocol Amendment 1 Final**LIST OF ABBREVIATIONS**

ADR	Adverse Drug Reaction
AE	Adverse Event
CP	Concept Protocol
CRF	Case Report Form
EoS	End of Study
EPI	Expanded Program on Immunization
GEP	Good Epidemiological Practice
GSK	GlaxoSmithKline
ICF	Informed Consent Form
IEC	Independent Ethics Committee
IRB	Institutional Review Board
LAR	Legally Acceptable Representative
LSOP	Local Standard Operating Procedure
MFDS	Ministry of Food and Drug Safety
PCD	Primary Completion Date
PI	Prescribing Information
PII	Personally Identifiable Information
PMS	Post-Marketing Surveillance
SAE	Serious Adverse Event
SDV	Source Document Verification
SOP	Standard Operating Procedure
SPM	Study Procedure Manual
VCSP	GSK Biologicals' Central Safety and Pharmacovigilance

**CONFIDENTIAL**208710 (EPI-HPV-077 VS KR PMS)  
Protocol Amendment 1 Final**GLOSSARY OF TERMS**

**Adequate contraception:** Adequate contraception is defined as a contraceptive method with failure rate of less than 1% per year when used consistently and correctly and when applicable, in accordance with the product label for example:

- abstinence from penile-vaginal intercourse, when this is their preferred and usual lifestyle,
- Combined estrogen and progesterone oral contraceptives, either combined or progestogen alone,
- injectable progestogen,
- implants of etenogestrel or levonorgestrel,
- Contraceptive oestrogenic vaginal ring,
- percutaneous contraceptive patches,
- intrauterine device or intrauterine system,
- male partner sterilisation prior to the female subject's entry into the PMS, and this male is the sole partner for that subject,

The information on the male sterility can come from the site personnel's review of the subject's medical records; or interview with the subject on her medical history.

- male condom combined with a vaginal spermicide (foam, gel, film, cream or suppository), and/or progesterone alone oral contraceptive.,
- male condom combined with a female diaphragm, either with or without a vaginal spermicide (foam, gel, film, cream, or suppository).

Adequate contraception does not apply to subjects of child bearing potential with same sex partners, or for subjects who are and will continue to be abstinent from penile-vaginal intercourse on a long term and persistent basis, when this is their preferred and usual lifestyle.

**Adverse drug reaction:** An adverse drug reaction is any adverse event whose causality to the drug cannot be ruled out and is assessed as "certain" or "probably/likely" or "possible" or "conditional/unclassified" or "unassessible /unclassifiable".

**CONFIDENTIAL**

208710 (EPI-HPV-077 VS KR PMS)  
Protocol Amendment 1 Final

Child in care:	A child who has been placed under the control or protection of an agency, organisation, institution or entity by the courts, the government or a government body, acting in accordance with powers conferred on them by law or regulation. The definition of a child in care can include a child cared for by foster parents or living in a care home or institution, provided that the arrangement falls within the definition above. The definition of a child in care does not include a child who is adopted or has an appointed legal guardian.
Eligible:	Qualified for enrolment into the PMS based upon strict adherence to inclusion/exclusion criteria.
End of Study (EoS):	For studies without collection of human biologicals samples or imaging data EoS is the Last Subject Last Visit (LSLV).
(Synonym of End of Trial)	For studies with collection of Human Biologicals Samples or imaging data, EoS is defined as the date of the last testing/reading released of the Human Biological Samples or imaging data, related to primary and secondary endpoints. EoS must be achieved no later than 8 months after LSLV.
Epoch:	An epoch is a set of consecutive time points or a single time point from a single protocol. Epochs are defined to support a main purpose which is either to draw conclusions on subject participation or to draw a complete conclusion to define or precise the targeted label of the product. Supporting means that data collected at the time points included in an epoch must be sufficient to fulfil the purpose of the epoch.  Typical examples of epochs are screening, primary vaccinations, boosters, yearly immunogenicity follow-ups, and surveillance periods for efficacy or safety.
eTrack:	GSK's tracking tool for clinical/epidemiology trials.
Evaluable:	Meeting all eligibility criteria, complying with the procedures defined in the protocol, and, therefore, included in the per protocol analysis.

**CONFIDENTIAL**

208710 (EPI-HPV-077 VS KR PMS)  
Protocol Amendment 1 Final

Expected adverse event:	The presence/occurrence/intensity of an AE that is expected from the subjects during the post-vaccination follow-up period as described in the locally approved Prescribing Information
Legally acceptable representative	An individual or juridical or other body authorized under applicable law to consent, on behalf of a prospective subject, to the subject's participation in the PMS.
(The terms legal representative or legally authorized representative are used in some settings.)	
Menarche:	Menarche is the onset of menses for the first time in a young female and is preceded by several changes associated with puberty including breast development and pubic hair growth. Menarche usually occurs within 1-2 years of breast development, thelarche. However, a young female can become pregnant before her first menses. Thus, a conservative definition of non-childbearing potential in a pre-menarcheal female is a young female who has not yet entered puberty as evidenced by lack of breast development (palpable glandular breast tissue).
Post-marketing surveillance:	Routine country-specific post vaccine/drug approval surveillance PMS mandated by regulatory authorities that applies an observational approach for the collection of safety information from subjects in a normal healthcare setting.
Primary completion date:	The date that the final subject was examined or received an intervention for the purpose of final collection of data for all primary outcomes, whether the clinical trial was concluded according to the pre-specified protocol or was terminated.
Prospective study:	A study in which the subjects/cases are identified and then followed forward in time in order to address one or more study endpoints.
Protocol amendment:	The International Conference on Harmonisation (ICH) defines a protocol amendment as: 'A written description of a change(s) to or formal clarification of a protocol.' GSK Biologicals further details this to include a change to an approved protocol that affects the safety of subjects, scope of the investigation, PMS design, or scientific integrity of the PMS.

**CONFIDENTIAL**208710 (EPI-HPV-077 VS KR PMS)  
Protocol Amendment 1 Final

Protocol administrative change:	A protocol administrative change addresses changes to only logistical or administrative aspects of the PMS.
Self-contained study:	Study with objectives not linked to the data of another study.
Subject number:	A unique number identifying a subject, assigned to each subject consenting to participate in the PMS.
Subject:	Term used throughout the protocol to denote an individual who has been contacted in order to participate or participates in the PMS.
Surveillance:	Surveillance is defined as the ongoing systematic collection, collation, analysis, and interpretation of descriptive epidemiological health data on a specific disease. Surveillance can monitor incidence and/or prevalence, and/or inform about when and where health problems are occurring and who is affected.
Unexpected adverse event:	Any AE that is not described in the approved Prescribing Information. Unexpected AEs are therefore not expected to occur during the post-vaccination follow-up period.

**CONFIDENTIAL**208710 (EPI-HPV-077 VS KR PMS)  
Protocol Amendment 1 Final**TRADEMARKS**

The following trademarks are used in the present protocol.

**Note: In the body of the protocol, the names of the vaccines will be written without the superscript symbol TM or ® and in *italics*.**

Trademarks of the GSK group of companies	Generic description
Cervarix	GlaxoSmithKline (GSK) Biologicals' Human papillomavirus (HPV) vaccine containing HPV-16/18 L1 virus-like particles (VLPs) and AS04 adjuvant

**CONFIDENTIAL**208710 (EPI-HPV-077 VS KR PMS)  
Protocol Amendment 1 Final

## 1. INTRODUCTION

### 1.1. Background

Anal cancer is rare in the general population with an average worldwide incidence of 1 per 100,000, but is reported to be increasing in more developed regions. Globally, there are an estimated 27,000 new cases every year [[de Martel C, 2012](#)]. Women have higher incidences of anal cancer than men. Incidence is particularly high among populations of men who have sex with men (MSM), women with history of cervical or vulvar cancer, and immunosuppressed populations, including those who are HIV-infected and patients with a history of organ transplantation.

In South Korea, the incidence of anal cancer by sex is 0.4 ASR (Age-standardized rates per 100,000 men per year) for men and 0.3 ASR (Age-standardized rates per 100,000 women per year) for women [[WHO/ICO HPV information center](#)].

Data on the role of Human papillomavirus (HPV) in anogenital cancers other than the cervix is limited, but there is an increasing body of evidence strongly linking HPV DNA with cancers of the anus, vulva, vagina, and penis. Although these cancers are much less frequent compared to cervical cancer, their association with HPV make them potentially preventable and subject to similar preventative strategies as those for cervical cancer. [[WHO/ICO HPV information center](#)].

HPV related anal cancer is predominantly associated with infection with HPV types 16 and 18 [[Chaturvedi, 2010](#)], that are included in *Cervarix*. This infers the possibility of using similar preventive strategies for both cancer types.

Based on two studies comparing the immunogenicity of *Cervarix* and *Gardasil* in females (HPV-010 and HPV-071) with two other studies (HPV-011 and HPV-040) providing immunogenicity and safety data for *Cervarix* vaccination in males, the indication of *Cervarix* was updated to include anal cancer caused by HPV types 16, 18 for both women and men by Ministry of Food and Drug Safety (MFDS) (Korea).

### 1.2. Rationale for the PMS

In Korea, GSK Biologicals' HPV vaccine containing HPV-16/18 L1 virus-like particles (VLPs) and AS04 adjuvant (*Cervarix*) was approved in July 2008. The indication was updated to include anal cancer caused by HPV types 16, 18 for both women and men. As per MFDS (Korea) requirements, this post-marketing surveillance (PMS) is being conducted to collect safety information on the use of *Cervarix* upon the expanded indication to anal cancer in both women and men, in at least 600 Korean women and men within 30 days after the vaccination when administered according to the approved Prescribing Information (PI) in Korea in a real health care setting over a 4-year period.

**CONFIDENTIAL**208710 (EPI-HPV-077 VS KR PMS)  
Protocol Amendment 1 Final**2. OBJECTIVE (AMENDED: 14 MAY 2018)**

To assess the safety of GSK Biologicals' HPV vaccine containing HPV-16/18 L1 virus-like particles (VLPs) and AS04 adjuvant, in terms of frequency and intensity of adverse events (AEs) and serious adverse events (SAEs) when administered according to the local PI.

Refer to Section 11.1 for the definition of the endpoint.

**3. PMS DESIGN OVERVIEW (AMENDED: 14 MAY 2018)**

Sequential Allocation of Subject Numbers					
Cervarix (N ~ 600)					
Vaccination Dose 1	Follow-up 30-day follow-up after Dose 1	Vaccination Dose 2	Follow-up 30-day follow-up after Dose 2	Vaccination Dose 3	Follow-up 30-day follow-up after Dose 3

N: Number of subjects planned to be enrolled

PMS conclusion will depend on the concluding visit of the subject in the PMS.

Definition of Conclusion of PMS for a subject: Subjects who have completed 30-day follow-up after at least one dose, regardless of the number of doses, are considered to have completed the PMS.

Note: Eligible subjects can be enrolled at any stage in the PMS regardless of Cervarix dose(s) received previously.

Follow-up for AEs will continue for 30 days after receiving each vaccine dose(s) in the PMS. Follow-up of SAEs will continue from the date of Visit 1 until 30 days after the last dose received in the PMS. Cervarix will be vaccinated according to local practice

Protocol waivers or exemptions are not allowed unless necessary for the management of immediate safety concerns. Therefore, adherence to the study design requirements, including those specified in the outline of study procedures (Section 8), are essential and required for study conduct. ***This PMS will be conducted by a continuous surveillance method.***

- PMS design: A prospective, observational, non-comparative, multi-centre PMS in Korea.
- Study population: 9-25 years old males and females.
- Vaccination schedule: Cervarix will be administered as per the local PI in Korea.

The recommended schedule is as follows:

- Vaccination: The 9-25 years old subjects should be administered Cervarix with 3 doses (**0.5mL each**), 0, 1, and 6 months schedule. The 9-14 years old subjects can be vaccinated with 2 doses, 0 and 6-12 months schedule. ***In the 2-dose schedule, if the second dose is administered before 5 months after the first dose, the third dose vaccination is required. In the 3 doses schedule, if the vaccination schedule requires flexibility, the second dose can be administered between 1 and 2.5 months and the third dose can be administered between 5 and 12 months after the first dose.***

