### **8.3. Detecting and recording AEs, ADRs and SAEs (Amended: 14 May 2018)**

#### **8.3.1. Time period for detecting and recording AEs, ADRs and SAEs**

All AEs and SAEs starting immediately following administration of each dose of *Cervarix* must be recorded onto the CRF and all SAEs must be reported using the PMS SAE reporting form, the latter to be sent to GSK according to the required timelines, irrespective of intensity or whether or not they are considered vaccination-related.

The standard time period for collecting and recording SAEs will begin at the first receipt of *Cervarix* in the PMS and will end 30 days (**Day 1 to Day 30**) after the last dose of *Cervarix* administered during the subject's participation in PMS. See Section 8.4 for instructions on reporting and recording SAEs.

An overview of the protocol-required reporting periods for AEs, ADRs and SAEs is given in **Table 4**.

**CONFIDENTIAL**208710 (EPI-HPV-077 VS KR PMS)  
Protocol Amendment 1 Final**Table 4 Reporting periods for AEs, ADRs and SAEs**

PMS activity	V1	29 days post-V1		V2	29 days post-V2		V3	29 days post-V3
Reporting of AEs (expected & unexpected)								
Reporting of SAEs/ADRs and Pregnancy*								

V: vaccination; Post-V: post-vaccination

\* For subjects who become pregnant after receiving *Cervarix* during PMS, the pregnancy outcome (whether full-term or premature, information on the status of the mother and child) of these subjects will be followed-up for 6-8 weeks after delivery, if possible.

Note: Post-vaccination adverse events will be collected and reported only for *Cervarix* doses received within the PMS (after signing the ICF). Any adverse events collected after *Cervarix* doses received outside of this PMS shall be reported as a spontaneous report and shall follow guidance for reporting of spontaneous report.

All AEs reported within 30 days of each dose of the vaccine administered within the PMS and all SAEs reported throughout the PMS period up to 30 days (**Day 1 to Day 30**) after the last dose of *Cervarix* administered during the subject's participation in the PMS need to be recorded in the CRF. These AEs/ SAEs will be classified as expected/unexpected at the time of statistical analyses (refer to [GLOSSARY OF TERMS](#) for definitions of expected/unexpected adverse events).

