All AEs reported during the 30 day (**Day 1 to Day 30**) follow-up period after each vaccine dose will be recorded using diary cards provided to the subjects or parent/LAR(s) of the subject. The AEs/SAEs will be analysed in the PMS report according to the expectedness and unexpectedness criteria as defined in the locally approved Prescribing Information (also refer to [GLOSSARY OF TERMS](#)).

Note: Assessment of causality and outcome will be done as defined in the MFDS (Korea) guidelines. According to the current version of MFDS (Korea) guidelines, causality will be assessed as: Certain; Probable/Likely; Possible; Unlikely; Conditional/Unclassified; Unassessable/Unclassifiable. Outcome will be assessed as recovered; not recovered; recovering; resolved with sequelae; fatal; unknown.

A post-surveillance AE/SAE is defined as any event that occurs outside of the AE/SAE reporting period defined in [Table 3](#). Physicians are not obligated to actively seek AEs/SAEs in former PMS participants. However, if the physician learns of any SAE, including a death, at any time after a subject has been discharged from the PMS, and he/she considers the event reasonably related to the *Cervarix*, the physician will promptly notify the Contact for Reporting SAEs.

**CONFIDENTIAL**208710 (EPI-HPV-077 VS KR PMS)  
Protocol Amendment 1 Final**8.3.2. Evaluation of AEs, ADRs and SAEs****8.3.2.1. Active questioning to detect AEs, ADRs and SAEs**

The physician needs to collect information on any AE in the subject. At the time of analysis, an assessment on whether the AE is expected (contained in the local PI) or unexpected (not contained in the local PI) will be done by GSK.

As a consistent method of collecting safety information, the subjects or subject's parent(s)/LAR(s) should be asked a non-leading question such as:

*'Have you/has your child acted differently or felt different in any way since receiving the vaccine or since the last visit'*

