**11. STATISTICAL METHODS****11.1. Endpoints (Amended: 14 May 2018)**

- Occurrence of AEs during the 30-day (**Day 1 to Day 30**) follow-up period after each vaccine dose.
- Occurrence of SAEs reported throughout the PMS period up to 30 days (**Day 1 to Day 30**) after the last dose administered during the subject’s participation in the PMS.

**CONFIDENTIAL**208710 (EPI-HPV-077 VS KR PMS)  
Protocol Amendment 1 Final

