#### **11.5.2. Analysis of safety**

Safety analysis based on total vaccinated cohort, will include all subjects who were vaccinated per product information and have completed 30-day follow-up after at least one dose, regardless of the number of dose. Analysis of AE/SAE data reported after each dose will be performed separately.

**CONFIDENTIAL**208710 (EPI-HPV-077 VS KR PMS)  
Protocol Amendment 1 Final**11.5.2.1. Within group assessment**

The AEs/ SAEs will be analysed in the PMS report according to the expectedness and unexpectedness criteria. (Refer to **GLOSSARY OF TERMS** for the definitions of expected AEs and unexpected AEs).

The number and percentage, with exact 95% confidence interval (CI), of any AEs occurring within 30 days (**Day 1 to Day 30**) will be tabulated, for each dose, for overall doses and by number of subjects. The same calculations will be done for any adverse events according to the severity and for those assessed as causally related to vaccination.

The verbatim reports of signs and symptoms will be matched and coded according to the appropriate WHO-ART Preferred Term. The PMS physician will review and confirm the appropriate WHO-ART Preferred Term by responding to data queries if any discrepancies are reported while coding. The percentage of subjects with AEs occurring within 30 days (**Day 1 to Day 30**) with its exact 95% CI will be tabulated by preferred term. Similar tabulation will be done for AEs with relationship to vaccination and for AEs rated as grade 3.

The number and percentage of subjects who received concomitant medication/ vaccination at least once during the 30-day (**Day 1 to Day 30**) follow-up period will be tabulated after each vaccine dose and overall, with exact 95% CI. Similar tabulations will be done for the number of subjects by types of medication/ vaccination during the entire PMS period.

The outcome of pregnancy (reported in the pregnancy report form) for subjects who become pregnant subjects during PMS will be presented, If possible.

Serious adverse events and withdrawals due to adverse events reported during the PMS period (each subject receiving the vaccine up to 30 days after the last dose) will be described in detail.

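### An SAE that starts after Day 30 of the latest PMS dose is inside the SAE period only if another dose follows, so fatal or vaccination-ending events in that gap can be lost from the SAE endpoint

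*Protocol*

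**What the plan says.** The two safety windows in Protocol Section 3 are built differently. For AEs: "Follow-up for AEs will continue for 30 days after receiving each vaccine dose(s) in the PMS". That window is fixed once a dose is given. For SAEs: "Follow-up of SAEs will continue from the date of Visit 1 until 30 days after the last dose received in the PMS". That window ends at a date known only when it is clear which dose was the last.

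The SAE rule recurs:
- Protocol 8.3.1 on collection: "The standard time period for collecting and recording SAEs will begin at the first receipt of" the vaccine in the PMS. The period closes 30 days after the last PMS dose.
- Protocol 11.1, one of only two endpoints: "Occurrence of SAEs reported throughout the PMS period up to 30 days" after the last dose given during participation.
- Protocol 11.5.2.1 describes SAEs and AE withdrawals over the same last-dose period.

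For anything later, 8.3.1 says: "A post-surveillance AE/SAE is defined as any event that occurs outside of the AE/SAE reporting period defined in" the cited table. It adds: "Physicians are not obligated to actively seek AEs/SAEs in former PMS participants". If the physician learns of an SAE or death after discharge, prompt notification is required only when it is considered reasonably related to the vaccine. Protocol 8.5.1 exempts pregnancy outcomes that are SAEs, which are always reported.

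Doses can be far apart. The standard course is 0, 1 and 6 months, and: "The 9-14 years old subjects can be vaccinated with 2 doses, 0 and 6-12 months schedule". Under Protocol 10.1 a subject is complete after one 30-day follow-up, however many doses were given.

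**The concern.** For an SAE in the gap between a 30-day window and the next dose, the rule uses the future to decide whether the event belongs to the period. Take two subjects on 0, 1, 6 months, each with the same SAE 90 days after dose 2. One recovers and receives dose 3, so the SAE is inside the period. The other is not vaccinated again because of the SAE, so dose 2 becomes the last dose, the period closed 30 days after it, and the SAE falls 60 days outside. A fatal event starting in the gap is always in the second position.

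This is selection on a consequence of the event itself, and it works in one direction: gap events compatible with another dose are kept, and the gravest can be lost. The whole-period SAE incidence then tends to be too low for the events that matter most. SAP 5.5 divides by subjects in the safety analysis set, not by person-time, so observation periods of very different length also enter one percentage.

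**Working it through.** The documents give no figure for the length of the SAE period, so there is none to reproduce. The check has two parts.

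**1. How much of the period depends on a later dose.** Inputs: the schedules in Protocol Section 3 and the Day 1-30 windows. Convention: one month = 30.44 days, so months 1, 2.5, 5, 6 and 12 fall on days 30, 76, 152, 183 and 365. The subject enters at dose 1.

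Full period = day of last dose + 30. Conditional days = full period − days inside any 30-day post-dose window.

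| Schedule (months) | Full period | In post-dose windows | Conditional | Share |
|---|---|---|---|---|
| 0, 1, 6 | 183 + 30 = 213 | 90 | 123 | 58% |
| 0, 1, 5 | 152 + 30 = 182 | 90 | 92 | 51% |
| 0, 2.5, 12 | 365 + 30 = 395 | 90 | 305 | 77% |
| 0, 6 | 183 + 30 = 213 | 60 | 153 | 72% |
| 0, 12 | 365 + 30 = 395 | 60 | 335 | 85% |

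A subject who stops after dose 1 has a 30-day period; one who stops after doses at 0 and 1 month has 60 days. Neither has conditional days. Section 3 allows enrolment at any stage, and a subject who enters at the final dose has no gap. Between doses at 0 and 1 month the gap is practically nil.

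**2. What could be lost.** Let q be the share of gap SAEs that end vaccination, including deaths. With a constant SAE rate, share of SAEs lost = q × conditional share. Neither q nor the SAE rate is in the documents, so these are assumptions.

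- q = 25%: 0.25 × 58% = 14% (0, 1, 6); 0.25 × 72% = 18% (0, 6); 0.25 × 85% = 21% (0, 12).
- q = 50%: 29%, 36% and 42%.
- Fatal events starting in the gap: q = 100% by construction.

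In subjects, with N = 600 all entering at dose 1 on 0, 1, 6 and rate λ per person-year: expected = 600 × (1 − exp(−λ × 213/365.25)); lost = q × 600 × (1 − exp(−λ × 123/365.25)). At q = 25%:

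| λ | Expected | Still counted | Loss, percentage points |
|---|---|---|---|
| 0.01 | 3.5 | 3.0 | 0.5/600 = 0.1 |
| 0.02 | 7.0 | 6.0 | 1.0/600 = 0.2 |
| 0.05 | 17.2 | 14.7 | 2.5/600 = 0.4 |

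If all 600 were instead on 0, 12, the same rates and q would take 6.5 to 5.1 (0.2 points) at the low end and 31.6 to 24.9 (1.1 points) at the high end. For scale, Protocol Table 6 gives an exact interval of 0.4% to 2.2% at an observed 1%.

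**The case against.** A reader might infer something stronger: that deaths and SAEs which stop vaccination drop out of the endpoint altogether, or that no death after Day 30 of a dose can count. The documents do not support either.

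- Such an event starting on Day 1-30 after any PMS dose is inside the period.
- A death 45 days after dose 1 and 15 days after dose 2 is also inside.
- Under Protocol 8.5, an SAE that starts inside the period is followed to its outcome, so a later death from it is captured.

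Nor does any section order removal of an SAE already on file because the next dose was not given. Protocol 8.4.4 requires a report within 24 hours for any SAE in a PMS subject, and 8.3.1 makes this irrespective of causality. The relief from active searching concerns former participants; someone awaiting a dose may not be one. Protocol 10.2.1 uses all data up to withdrawal or last contact. SAP 6.8.2 sets no upper time limit on its tables and lists AEs behind a missed visit. SAP 6.8.1 already provides separate Day 1-30 SAE analyses after each dose, which fits the rationale in Protocol 1.2 of safety within 30 days. The surveillance is descriptive, and the loss shares are assumed.

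All of that stands, and it limits the point, but it does not settle it. Protocol 10.1 lets a subject count as complete after one 30-day window, so a subject in the gap may or may not be treated as discharged. Diary cards cover 30 days and the scheduled visits are vaccination visits, so someone who never returns may not be asked about the gap. Protocol 11.5.2.1 restricts the description of SAEs and AE withdrawals to the last-dose period, while SAP 6.8.2 does not. One site could record a gap SAE and another leave it out, each with text to cite.

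**Conclusion.** The point holds for SAEs and deaths with onset after Day 30 of the most recent PMS dose and no later dose. By the wording of the period and endpoint they are outside; if one happens to be recorded before discharge, other provisions could keep it, so inclusion would vary by site. The error runs towards missing fatal and vaccination-ending events. Of the non-pregnancy events, no section clearly brings these back.

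The day shares of 58%, 72% and 85% follow from the schedules for subjects entering at dose 1 and are lower once later entrants are mixed in. The 14% loss on 0, 1, 6, and its equivalent of roughly 0.1-0.4 percentage points of 600 subjects, rest on an assumed q of 25%, a constant rate and 1-5 SAEs per 100 person-years. In absolute terms this is a handful of events at most on that schedule, but with so few expected each omission counts. The per-dose Day 1-30 SAE results are sound. This is a should-fix point, not a threat to the surveillance as a whole.

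**What to change.** 1. In Protocol 11.1 and SAP 6.8.1, make the already planned SAE incidence, with exact 95% CI, for onset on Day 1-30 after each PMS dose the SAE endpoint figure. That window does not depend on later dosing, so the conditional days fall to zero.
2. In Protocol 8.3.1 and SAP 6.8.2, state that every SAE or death the site learns of from the first PMS dose to the end of the study is recorded and listed separately, with days since the last dose, whatever the causality and whether or not another dose was given.
3. Amend the post-surveillance paragraph in 8.3.1 to agree with this, and bring Protocol Section 3 and 11.5.2.1 into line.

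No vaccination rule changes. The cost is protocol and SAP wording, one extra listing, a few more SAE records at sites, and SAE counts that may look slightly less favourable.
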